**Keys to Abbreviations:**

- A = Verify no change in medical history, subject still meets all study inclusion/exclusion criteria
- B = If performed at the screening visit, must be performed when subject exit the study
- C = In a subject where both eyes qualified at Visit 2, if a plug is extruded in one eye, **plug is to be replaced** and subject continues in the study
- D = In a subject where only one eye qualified at Visit 2, if the plug is extruded in the qualified eye, the subject will be DISCONTINUED and replaced. In a subject where both eyes qualified, if a plug is extruded in one eye, then extruded again or in the fellow eye, the subject will be DISCONTINUED and replaced
- \* = Plug position evaluated after eye exam and plug insertion
- ‡ = If subject EXITs the study after visit 2, but before visit 7, subject must return to Investigator's office to have plugs removed

Body Temperature:	Temperature maybe taken using a non-contact (Infrared) thermometer or orally. Oral temperatures should not be taken within five minutes of ingestion of any food or drink
Heart Rate:	Heart rate taken in the sitting position after subject has rested for 5 minutes. Recorded values can be obtained electronically (automated) or manually (observed for 30 seconds or more)
Blood Pressure:	Blood pressure, taken in the sitting position after subject has rested for 5 minutes. Recorded values can be obtained electronically (automated) or manually
Plug Position Evaluation:	Position of the plug will be evaluated as either: Normal, Present but requires adjustment, Extruded/Recovered, Extruded/Lost, Other
Slit-Lamp Exam:	Evaluation will include the Lids (Upper & Lower), Conjunctiva (Bulbar & Palpebral) and the Cornea. SL Findings will be graded on a 5-point scale: 0 = None, 1 = Trace, 2 = Mild, 3 = Moderate, 4 = Severe
IOP Evaluation:	Goldmann applanation tonometry will be used for measuring IOP. Just prior to the start of the study, the tonometer should be calibrated. IOP of each eye will be measured twice, alternating between the eyes. The average of the two measurements will be used for analysis. However, if there is a $\geq 3$ mmHg difference between the 1 st and 2 nd measurement for an eye, a 3 rd measurement will be taken and the average of the two closest values of the three will be used for analysis for that eye.

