### 5.2.3 Study Treatment Phase Criteria

#### 5.2.3.1 Treatment Phase - INCLUSION Criteria:

After the washout phase, the following are requirements a subject must meet in order to be considered for enrollment into the treatment phase of the study:

- 1) After the six-week washout phase, the subject continues to meet all screening phase inclusion/exclusion criteria
- 2) After the six-week washout phase, subject's Baseline (Visit 2) IOP, measured between 8:00 and 10:00 AM, is  $\geq 23.0$  and  $\leq 34.0$  mmHg in at least one eye

- 3) Subject's Baseline (Visit 2, morning average) IOP is  $\geq$  5 mmHg from the subject's SCREENING (pre-washout) IOP in at least one eye whose Baseline IOP is between  $\geq$  23 and  $\leq$  34 mmHg.
- 4) Investigator is able to dilate the lower puncta of each eye to 1.0 mm, and insert a study plug into each puncta.

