- h. Automated Perimetry (visual fields) will be measured using a Humphrey's Visual Field Analyzer (manufactured by Carl Zeiss Meditec Inc., Dublin, CA) with at least a standard full-threshold 24-2 program or Swedish interactive threshold algorithm (SITA) program. **Visual fields measured and documented up to SIX months before the Screening Visit are acceptable** to fulfill the screening criteria
  - i. Pachymetry can be measured by contact methods, such as ultrasound and confocal microscopy (CONFOSCAN), noncontact methods such as optical biometry with a single Scheimpflug camera (such as SIRIUS or PENTACAM), dual Scheimpflug camera (such as GALILEI), or Optical Coherence Tomography (OCT), such as Visante. **Past corneal thickness measurement documented in the subject's chart** are acceptable to fulfill the screening criteria
  - j. Slit-Lamp Examination: Examination will include assessment of the lid, conjunctiva and cornea. Grading of slit-lamp findings are defined in [Appendix C](#).
  - k. Perform a NON-DILATED fundus exam of each eye. Using an ophthalmoscope, the investigator will examine the back part of the eye (fundus), including the retina, optic disc, choroid and blood vessels and evaluation of the lens
  - l. Goldmann applanation tonometry will be used for measuring IOP. IOPs will be measured in the morning between 8:00 and 10:00 am. The IOP of each eye will be measured twice, alternating between the eyes. However, if the second measurement is  $\geq \pm 3$  mmHg from the first measurement for an eye, a third measurement will be taken. All measurements taken will

be recorded. In the case of two measurements, the average of the two values will be used for analysis, and in the case of three measurements, the average of the two closest values of the three will be used for analysis for that eye at that specific time point.

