#### 10.4.2 Analysis of Primary Study Variable

The primary study outcome variable will be the change in IOP at Visits 4, 5, 6 and 7 (Days 7, 28, 60 and 90 days post-insertion) compared with the Baseline IOP (Visit 2, Day 0), obtained between 8:00 and 10:00 AM. The unit of analysis will be the study eye at visit 2 with the highest post-washout IOP. Observed IOP and percent change from baseline in IOP will also be analyzed.

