**Figure 4**

Applanation tonometry semi-circles viewed through the Goldmann Prism

Correct end point:(diagram "B"):  
Inner edges of the semi-circles  
are just touching ("kissing")

After the tonometer has been withdrawn, read and record the pressure from the scale on the knob on the side of the tonometer, then reset the tonometer knob to "10" (NOTE: Whenever possible,

the same individual should perform and record the pressure values from the tonometry, at each time point for all subjects).

The IOP of each eye will be measured twice, alternating between eyes. However, if the second measurement is  $\geq \pm 3$  mmHg from the first measurement for an eye, a third measurement will be taken. All measurements taken will be recorded. In the case of two measurements, the average of the two values will be used for analysis, and in the case of three measurements, the average of the two closest values of the three will be used for analysis for that eye at that specific time point.

[figure not shown]

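### When a third IOP reading is taken, averaging the two closest values is undefined for equally spaced readings and less precise than the median of the same three readings (minor, near-free improvement)

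*Combined protocol and SAP*

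**What the plan says.** Section 7.2.1(l) has IOP read twice per eye. For two readings, "In the case of two measurements, the average of the two values will be used for analysis". If the second is at least 3 "mmHg from the first measurement for an eye, a third measurement will be taken", and then "in the case of three measurements, the average of the two closest values of the three will be used for analysis for that eye". Appendix D repeats this, and the keys under both schedules of assessments (Study Synopsis and Section 7.4.3.6) state the same rule: "the average of the two closest values of the three will be used for analysis for that eye". None of the four places says what to do when the three readings are equally spaced. Appendix D adds: "All measurements taken will be recorded".

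The resulting value is used three times:

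- **Entry.** Section 5.2.3.1 begins "After the six-week washout phase, subject's Baseline (Visit 2) IOP, measured between 8:00 and 10:00 AM, is" and sets limits of 23.0 to 34.0 mmHg in at least one eye. It also asks for a difference of at least 5 mmHg from screening.
- **Choice of analysis eye.** Section 10.4.2 takes the eye with the highest post-washout pressure.
- **Primary outcome.** "The primary study outcome variable will be the change in IOP at Visits 4, 5, 6 and 7", relative to Visit 2.

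**The concern.** A third reading exists only when the first two disagree. It then usually falls between them, so the rule averages it with one of the two discordant values and discards the other. This has two consequences.

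First, when the third reading lies exactly midway, or the three are otherwise equally spaced, two different values both comply with the protocol. With whole-mmHg readings and a trigger of 3 mmHg, the spacing in any tie is at least 2 mmHg, so the two permitted values differ by at least 2 mmHg. At Visit 2 that can move an eye across an entry limit or change which eye is analysed. In a single-arm study, taking the higher value at baseline also enlarges the apparent fall.

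Second, discarding one of two discordant readings costs precision in the primary outcome when the discordance is ordinary measurement error and not a misreading.

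**Working it through.** **Inputs from the documents.** The trigger (difference of 3 mmHg or more), the two-closest rule, the entry limits of 23.0 and 34.0 mmHg, and up to 30 subjects. The plan gives no reading SD, reading resolution, SD of IOP change or power figure, so there is no figure of its own to reproduce.

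**Assumptions.** Whole-mmHg readings; independent reading errors with SD s of 1.0, 1.5 or 2.0 mmHg; SD of IOP change 3.5 mmHg. For comparison, the IZBA label in Appendix K gives an 8 AM Month 3 change of -8.2 (-8.6, -7.9) with n = 432, which implies an SD of about 0.35/1.96 × √432 = 3.7 mmHg.

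**Step 1: ties.** These examples need no assumed SD.

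- 21, 25, 23: (21 + 23)/2 = 22 or (23 + 25)/2 = 24. The first fails the 23 mmHg limit and the second meets it. The median is 23.
- 33, 37, 35: (33 + 35)/2 = 34 or (35 + 37)/2 = 36, on either side of the 34 mmHg limit. The median is 35.

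**Step 2: precision at three-reading visits.** Eye-visits were simulated (millions per setting), those with |r1 − r2| ≥ 3 were kept, and ties under the current rule were split at random. Entries are mean squared error (MSE) in mmHg². The last column is the reduction in moving from two-closest to the median, from unrounded values.

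| Error model | s | First two only | Two closest | Median | Mean of three | Reduction |
|---|---|---|---|---|---|---|
| Normal | 1.0 | 0.54 | 1.34 | 0.81 | 0.36 | 39% |
| Normal | 1.5 | 1.17 | 2.20 | 1.39 | 0.78 | 37% |
| Normal | 2.0 | 2.04 | 3.38 | 2.16 | 1.36 | 36% |
| 5% of readings with SD 4 | 1.0 | 3.12 | 1.39 | 1.00 | 1.59 | 28% |
| 5% of readings with SD 4 | 1.5 | 2.22 | 2.37 | 1.57 | 1.32 | 34% |
| 5% of readings with SD 4 | 2.0 | 2.64 | 3.61 | 2.34 | 1.69 | 35% |
| 5% of readings off by 8 | 1.0 | 9.45 | 2.21 | 1.82 | 4.67 | 18% |
| 5% of readings off by 8 | 1.5 | 6.03 | 2.89 | 2.20 | 3.29 | 24% |
| 5% of readings off by 8 | 2.0 | 5.50 | 4.25 | 2.98 | 3.26 | 30% |

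Analytic check: under normal error the mean of two readings is independent of their difference, so its MSE after the trigger should stay at s²/2 plus about (1/12)/2 = 0.04 for rounding. That gives 0.54, 1.17 and 2.04, as simulated.

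**Step 3: how often (normal error).** Third readings occur at 8.3%, 24.3% and 37.9% of eye-visits for s = 1.0, 1.5 and 2.0. Of these, 5.2%, 8.0% and 9.2% tie, which is 0.4%, 1.9% and 3.5% of all eye-visits. With true IOP assumed to have mean 25 and SD 3, ties straddling 23 or 34 mmHg occur at 0.08%, 0.43% and 0.89% of eye-visits. Per 60 eyes measured at Visit 2, that is about 0.05 to 0.5 eyes.

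**Step 4: effect on the primary outcome.** The change uses two visits, so the share of variance saved is 2 × P(third reading) × (MSE two-closest − MSE median) / 3.5².

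- s = 1.0: 2 × 0.083 × 0.53 / 12.25 = 0.7%
- s = 1.5: 2 × 0.243 × 0.81 / 12.25 = 3.2%
- s = 2.0: 2 × 0.379 × 1.22 / 12.25 = 7.6%

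At s = 1.5 and n = 30, the half-width of a 95% interval for the mean change moves from about 1.31 to 1.29 mmHg.

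**The case against.** The strongest defence is that the trigger singles out discordant readings, so gross misreadings are the relevant case and the two-closest rule guards against them. That stands in part. At s = 1.0 with 5% of readings at SD 4, the rule has MSE 1.39 against 3.12 for the first two readings alone; with 8 mmHg errors it has 2.21 against 9.45. A reader might infer that the rule is always worse than ignoring the third reading. That holds under normal error but not in these cases. The defence does not favour two-closest over the median, however, because the median is better in every row of the table.

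A reader might also infer that the median cures the imprecision. It does not. Under normal error it remains noisier than the mean of the first two (0.81 against 0.54, 1.39 against 1.17, 2.16 against 2.04). The mean of all three also has a single value and is quieter under normal error. It does worse than the median with 8 mmHg errors at every s, and with SD 4 outliers at s = 1.0, but better with SD 4 outliers at s = 1.5 and 2.0. The choice between these two therefore depends on an error model that the documents do not give.

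Finally, a reader might infer that an unmasked investigator can choose who is eligible. The documents do not support that as a material risk. Straddling ties are rare, one qualifying eye is enough, and the 5 mmHg criterion applies as well. Every reading is recorded, and Section 11.4 has the case report forms checked against source, so a choice would be visible. Nor does the median remove discretion: at 69-91% of three-reading visits (normal error, s from 2 down to 1) it equals the third reading, taken by someone who has seen the first two.

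**Conclusion.** The point holds as a minor one. The rule does not always define a value for a measure that decides entry, the analysis eye and the primary outcome; that follows from the text alone. Its loss of precision relative to the median is consistent across the error models tried, at 18% to 39% of MSE at three-reading visits. The size rests on an assumed reading SD of 1 to 2 mmHg and whole-mmHg readings. Appendix D asks for the same evaluator and tonometer and monthly calibration, which favours the lower end.

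The consequence for the trial is small: about 1% to 8% of the variance of IOP change, and at most about 0.9% of eye-visits with a tie across an entry limit. In a pilot of up to 30 subjects this will not alter the conclusions. It is worth changing because the replacement costs almost nothing.

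**What to change.** In Section 7.2.1(l), Appendix D and both schedule keys, state that if a third measurement is taken, the median of the three recorded values is used for eligibility and for analysis. This is one sentence in four places, with no added readings or forms, and analysis values can be recomputed from data already recorded. If the sponsor prefers the mean of all three, that also removes ties, with less protection against a large misreading. If the two-closest rule is kept, the minimum is an explicit tie rule.

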**NOTE: Just prior to the start of the study, the tonometer should be calibrated.**

- m. Punctal size evaluation and dilation of the punctum (see Appendices E & F for details),
- n. Insertion and removal of study punctal plugs (see Appendix G & H for details)
- o. Adverse Event/Adverse Device Event reporting, [Section 8.7](#) of the protocol for details: To optimize consistency of AE/ADE reporting across centers, the study subject will be asked a standard question to elicit any AE/ADEs. At each study visit or telephone evaluation of the study subject, study personnel will ask the following question:

**“Have you had any problems since your last visit?”**

#### 7.2.2 Standard of Care Procedures

At any study visit (scheduled or unscheduled), in addition to study specific examinations the Investigator will perform their standard evaluations for an OAG or OH patient.

### 7.3 Laboratory Procedures/Evaluations

Not applicable

### 7.4 Study Visit Phases/Schedule

#### 7.4.1 Visit 1 - Screening Phase (Qualification Visit)

At this visit, prior to any study specific procedure or examination, a subject must read, comprehend and give written Authorization for Use/Disclosure of Health Information (HIPAA) and Informed Consent to participate in the study. Once all forms have been signed, the investigator and/or his or her staff will perform the following screening assessments/examinations.

- a. Verify a subject has not used any hypotensive ocular drops within the last 12 hours of the screening visit
- b. A female subject of child-bearing potential will have a urine pregnancy test performed
- c. Record subject's demographic data and medical history for past 6 months
- d. Measure subject's temperature, heart rate and blood pressure
- e. Record subject's Best-Corrected (Glasses) Distance or Pinhole Visual Acuity
- f. Verify automated perimetry results have been measured and documented in the subject's chart within the last 6 months

**NOTE:** If perimetry measurement are older than 6 months, perform automated perimetry at the screening visit

g. Verify corneal thickness measurements are documented in the subject's chart

**NOTE:** If corneal thickness data is not available, measure corneal thickness of each eye using contact or non-contact pachymetry at the screening visit

h. Perform a slit-lamp examination of each eye

i. Perform a non-dilated fundus exam of each eye, including the evaluation of the lens

j. Record IOP measurement of each eye

k. Record concomitant medication use

If at any time during the screening examination it is determined a subject does not meet a screening inclusion/exclusion criterion, at that point any additional screening assessments-examinations will be discontinued.

After the screening procedures and examinations have been completed, each qualified subject that meets all study inclusion/exclusion criteria will be asked to enter the washout phase of the study and will be sequentially assigned an ID number ([Section 6.1](#)). In addition, the ID number and the study subject initials will be recorded on study case report forms, in lieu of recording his/her name, in order to maintain subject confidentiality.

#### 7.4.2 Washout Phase (Six-week duration)

During the washout phase of the study, each subject will be instructed to discontinue the use of his/her topical hypotensive medication(s) for the next six-weeks. In addition, the subject will be instructed not to use any other ocular drops, gels or ointments 24 hours prior to the Baseline visit (Visit 2) in his/her eyes that have not been prescribed by the investigator.

Systemic or topical medications that are being used at the Screening Visit, that are considered necessary for the subject's welfare and are PERMITTED by the protocol ([Sections 5.2.1](#)), may continue to be used as long as the concentration and dosing frequency of the medication(s) will remain the same throughout the entire duration of the study.

Systemic medications that are PROHIBITED by the protocol, must be discontinued during the washout phase. All ocular drops, gels or ointments being used by the subject must be discontinued 24 hours prior to Visit 2. Should the subject qualify for the treatment phase of the study, they will be asked to continue for an additional  $90 \pm 7$  days not to use any systemic or topical medications during the treatment phase of the study.

#### 7.4.3 Treatment Phase (Visits 2, 3, 4, 5, 6 & 7)

At the completion of the washout phase (6-weeks) each subject that continues to meet all study screening, washout and baseline criteria will have the lower puncta of each eye inserted with a Travoprost Evolute® and scheduled to return to the investigator's office for follow-up examinations at one, seven, 28, 60 and 90 days after insertion of the study plugs.

#### 7.4.3.1 Visit 2 - Day 0, Plug Insertion Visit (Baseline)

Qualified subject will undergo the following:

- a. Verify a subject has not used any hypotensive ocular drops during the washout phase
- b. Verify whether there are any changes in the medical history and confirm the subject still meets all study inclusion/exclusion criteria
- c. Record any addition, discontinuation or changes in the subject's use of any concomitant medications or ocular drops, gels or ointments during study washout phase
- d. Record subject's temperature, heart rate and blood pressure
- e. Record subject's Best-Corrected (Glasses) Distance or Pinhole Visual Acuity
- f. Perform a slit-lamp examination of each eye
- g. Record IOP measurement for each eye
- h. Record any Adverse Events/Adverse Device Event.

After the baseline procedures and examinations have been completed, a subject that meets the baseline IOP inclusion criteria ([Section 5.2.3](#)) will have their punctal size of each eye evaluated and will be inserted with a Travoprost Evolute into the lower puncta of each eye even if only one eye qualifies.

- i. Dilate the lower puncta to 1.0 mm and insert a study plug into the lower punctum of each eye (refer to Sections [6.1.5.2](#) & [6.1.5.3](#) for details regarding punctum dilation and punctal plug insertion techniques)
- j. Evaluate after insertion, the position of the study plugs in each eye using the slit-lamp

**NOTE:** At the conclusion of the visit a subject does not meet all treatment inclusion/exclusion criteria or the investigator is unable to insert a Travoprost Evolute into the lower puncta of each eye, the study subject will be discontinued from the study. The subject ID number will be retired. If the investigator was able to insert only one study plug, the one inserted study plug must be removed ([Section 5.4](#))

Each study subject will be instructed not to attempt to remove or adjust the punctal plug on his/her own. In addition, encourage each study subject to restrict eye rubbing, swimming, scuba diving, or other actions or activities that may result in physical manipulation of the eye region

Each study subject will be scheduled to return the next day for a follow-up study examination (Visit 3, day 1 post-plug insertion).

**NOTE:** At any time during the treatment phase, a study subject has noticed a plug has been extruded or lost they should immediately contact the Investigator and/or his/her staff and return to the Investigator's office as soon as possible ([Section 6.1.8.2](#)).

#### 7.4.3.2 Visit 3 - Day 1, Post-Plug Insertion

- a. Verify a subject has not used any hypotensive ocular drops since his/her last visit
- b. Record any addition, discontinuation or changes in the subject's use of any concomitant medications or ocular drops, gels or ointments since his/her last visit
- c. Record subject's temperature, heart rate and blood pressure
- d. Record subject's Best-Corrected (Glasses) Distance or Pinhole Visual Acuity
- e. Evaluate the position of each Travoprost Evolute® using the slit-lamp
- f. Perform a slit-lamp examination of each eye
- g. Record IOP measurement for each eye
- h. Record any Adverse Events/Adverse Device Event

**NOTE:** Should a study subject exit the study early (after Visit 2 and before Visit 7), the subject must undergo all test and procedures scheduled for Visit 7 (Final Visit).

#### 7.4.3.3 Visit 4 - Day 7 ± 1, Post-Plug Insertion

- a. Verify a subject has not used any hypotensive ocular drops since his/her last visit
- b. Record any addition, discontinuation or changes in the subject's use of any concomitant medications or ocular drops, gels or ointments since his/her last visit
- c. Record subject's temperature, heart rate and blood pressure
- d. Record subject's Best-Corrected (Glasses) Distance or Pinhole Visual Acuity
- e. Evaluate the position of each Travoprost Evolute® using the slit-lamp
- f. Perform a slit-lamp examination of each eye
- g. Record IOP measurement for each eye
- h. Record any Adverse Events/Adverse Device Event

**NOTE:** Should a study subject exit the study early (after Visit 2 and before Visit 7), the subject must undergo all test and procedures scheduled for Visit 7 (Final Visit).

